#### 6.1.3 Pancreatic conditions

Amylase and lipase elevations have been observed in clinical studies with cabozantinib. The clinical significance of asymptomatic elevations of enzymes is not known but in general has not been associated with clinically apparent sequelae. It is recommended that participants with lipase elevation and/or symptoms of pancreatitis have more frequent laboratory monitoring of lipase and/or amylase (2-3 times per week). Participants with symptomatic pancreatitis should be treated with standard supportive measures.

#### 6.1.4 Asymptomatic lipase or amylase elevations

Asymptomatic Lipase or Amylase Elevations	
Grade 1 or Grade 2	Continue at current dose level. More frequent monitoring is recommended.
Grade 3	
 
If the participant is symptomatic, interrupt treatment. Treatment may be continued at the investigator's discretion if the participant is asymptomatic (i.e., no clinical or imaging evidence of pancreatitis).
 
Monitor lipase and amylase twice weekly.
 
Upon resolution to Grade ≤1 or baseline, cabozantinib may be restarted at the same dose or at a one-dose-level reduced dose provided that this occurs within 3 weeks.
 
If retreatment following Grade 3 lipase or amylase elevation is at the same dose and Grade 3 or Grade 4 elevations recur, then treatment must be discontinued.
 

Asymptomatic Lipase or Amylase Elevations	
	interrupted again until lipase and amylase levels have resolved to Grade $\leq 1$ or baseline and retreatment must be at a one-dose-level reduced dose.
Grade 4	
 
Interrupt treatment
 
Monitor lipase and amylase twice weekly
 
Upon resolution to Grade <math>\leq 1</math> or baseline and if resolution occurred within 4 days, cabozantinib may be restarted at the same dose or a one-dose-level reduced dose. If resolution took more than 4 days, the dose must be reduced by one-dose-level upon retreatment provided that resolution occurred within 3 weeks.
 
If retreatment following Grade 4 lipase or amylase elevation is at the same dose and Grade 3 or 4 elevations recur, then treatment must be interrupted again until lipase and amylase have resolved to Grade <math>\leq 1</math> or baseline and retreatment must be at a one-dose-level reduced dose.
 

#### 6.1.5 Pancreatitis

Pancreatitis	
Grade 2 and asymptomatic	
 
Continue at current dose level. More frequent monitoring of lipase and amylase and radiographic evaluation is recommended.
 

Grade 2 symptomatic and Grade 3	
 
Interrupt treatment
 
Monitor lipase and amylase twice weekly
 
Upon resolution to Grade <math>\leq 1</math> or baseline, cabozantinib may be restarted at a one-dose-level reduced dose if resolution occurred within 3 weeks
 

Grade 4	Permanently discontinue treatment. However, if the subject was unequivocally deriving benefit from cabozantinib therapy, treatment may resume at a reduced dose to be determined with Study Chair approval.

#### 6.1.6 Skin disorders

Palmar-plantar erythrodysesthesia syndrome (PPE; also known as hand-foot syndrome), skin rash (including blister, erythematous rash, macular rash, skin exfoliation, dermatitis acneiform, and papular rash), pruritus, dry skin, erythema, pigmentary changes, and alopecia have been reported in cabozantinib-treated participants. All participants on study should be advised to use prophylactic measures for skin care. These measures include the use of hypoallergenic moisturizing creams, ointment for dry skin, sunscreen with SPF  $\geq 30$ ; avoidance of exposure of hands and feet to hot water; protection of pressure-sensitive areas of hands and feet; and use of thick cotton gloves and socks to prevent injury and to keep the palms and soles dry. Participants with skin disorders should be carefully monitored for signs of infection (e.g., abscess, cellulitis, or impetigo).

Early signs of hand-foot syndrome can include tingling, numbness, and slight redness or mild hyperkeratosis. Early manifestations include painful, symmetrical red and swollen areas on the palms and soles. The lateral sides of the fingers or periungual zones may also be affected. Adequate interventions are required to prevent worsening of skin symptoms such as blisters, desquamations, ulcerations, or necrosis of affected areas. Aggressive management of symptoms is recommended, including early dermatology referral.

Treatment guidelines for PPE related to study treatment are presented in the table below.

In the case of study treatment-related skin changes (e.g., rash, hand-foot syndrome), the investigator may request that additional assessments be conducted with the participant's consent. These assessments may include digital photographs of the skin changes and/or a biopsy of the affected skin and may be repeated until the skin changes resolve.

Hand-Foot Skin Reaction and Hand Foot Syndrome (PPE)	
Grade 1	Continue cabozantinib at current dose if tolerable or reduce to the next lower dose if intolerable. Start urea 20% cream twice daily AND clobetasol 0.05% cream once daily. Assess subject at least weekly for changes in severity. Subjects should be instructed to notify investigator immediately if severity worsens. If severity worsens at any time or if there is no improvement after 2 weeks, proceed to the management guidelines for Grade 2 PPE.
Grade 2	
"Tolerable" Grade 2 PPE            Continue cabozantinib at current dose if tolerable. Start urea 20% cream twice daily AND clobetasol 0.05% cream once daily. Assess subject at least weekly for changes in severity. Subjects should be instructed to notify investigator immediately if severity worsens.
 
"Intolerable" Grade 2 PPE            Interrupt dosing. Start/continue urea 20% cream twice daily AND clobetasol 0.05% cream once daily. Add analgesics for pain control with NSAIDs/GABA agonists/narcotics if needed. Assess subject at least weekly for changes in severity. Subjects should be instructed to notify investigator immediately if severity worsens. If severity worsens at any time, or affects self-care, or if there is no improvement after 2 weeks, proceed to the management guidelines for Grade 3 PPE. If the dose was interrupted, treatment may continue or treatment may be restarted at a reduced dose at the discretion of the investigator upon resolution to Grade 0 or Grade 1 at one dose level lower. If intolerable PPE recurs without dose reduction, the dose should be interrupted, and resumed at one dose level lower following resolution.

Grade 3	Interrupt study treatment until severity decreases to Grade 1 or 0. Start/continue urea 20% cream twice daily AND clobetasol 0.05% cream once daily. Pain control with NSAIDs/GABA agonists/narcotics. Treatment may restart at one dose level lower when reaction decreases to Grade 1 or 0. Permanently discontinue subject from study if reactions worsen or do not improve within 3 weeks.

GABA,  $\gamma$ -aminobutyric acid; NSAID, nonsteroidal anti-inflammatory drugs; PPE, palmar-plantar erythrodysesthesia

#### 6.1.7 Embolism and thrombosis

Deep vein thrombosis and pulmonary embolism (PE) have been observed in clinical studies with cabozantinib; including fatal events (please refer to the IB). Participants who develop a PE or DVT should have study treatment held until therapeutic anticoagulation with heparins is established. Study treatment may be resumed with a one dose-level reduction in participants who have uncomplicated PE or DVT and are deriving clinical benefit from study treatment. During treatment with anticoagulants, participants need to be monitored on an ongoing basis for bleeding risk and signs of bleeding. Participants with life-threatening PE

or DVT should have study treatment discontinued unless toxicity can be managed and participant is deriving clear clinical benefit as determined by the investigator and agreed by the Study Chair. Venous filters (e.g., vena cava filters) are not recommended due to the high incidence of complications associated with their use. Once a participant is fully anticoagulated, treatment can be restarted per investigator judgment at one dose lower. Participants should permanently discontinue after a second thrombotic event. Although routine prophylactic anticoagulation is not necessary for all participants, prophylactic anticoagulation is allowed for individual participants at the discretion of the investigator.

Arterial thrombotic events (e.g., transient ischemic attack, myocardial infarction) have been observed rarely in studies with cabozantinib. Cabozantinib should be discontinued in participants who develop an acute MI or any other clinically significant arterial thromboembolic complication.

#### 6.1.8 Hypertension

Hypertension is a relatively common complication of other VEGF-pathway inhibitors and has been observed in cabozantinib clinical studies.

Decisions to decrease or hold the dose of study treatment must be based on BP readings taken by a medical professional and must be confirmed with a second measurement at least 5 minutes following the first measurement. Participants with known hypertension should be optimally managed prior to study entry. Clinical judgment should be used in deciding whether new or worsened hypertension emerging during treatment with cabozantinib requires immediate therapy, or whether therapeutic intervention can be delayed in order to confirm the finding of new or worsened hypertension at a second visit before taking new therapeutic action. It is recommended that this second visit occur within 1 week. Blood pressure should be monitored in a constant position visit to visit, either sitting or supine. Cabozantinib dosing should be interrupted in participants with severe hypertension (180 mm Hg systolic or 120 mm Hg diastolic; or sustained  $\geq 160$  mm Hg systolic or  $\geq 110$  diastolic) who cannot be controlled with medical interventions and discontinued in participants with hypertensive crises or hypertensive encephalopathy (see next Table below).

#### Management of hypertension related to Cabozantinib

Criteria for Dose Modifications	Treatment/Cabozantinib Dose Modification
Subjects not receiving optimized anti-hypertensive therapy	
$> 140$ mm Hg (systolic) and $< 160$ mm Hg OR $> 90$ mm Hg (diastolic) and $< 110$ mm Hg	
 
• Increase antihypertension therapy (i.e., increase dose of existing medications and/or add new antihypertensive medications).
 
• Maintain dose of cabozantinib.
 
• If optimal antihypertensive therapy (usually to include 3 agents) does not result in blood pressure <math>< 140</math> systolic or <math>< 90</math> diastolic, or if the subject is symptomatic, the dose of cabozantinib
 

Criteria for Dose Modifications	Treatment/Cabozantinib Dose Modification
	should be reduced by one dose level.
$\geq 160$ mm Hg (systolic) and $< 180$ mm Hg OR $\geq 110$ mm Hg (diastolic) and $< 120$ mm Hg	
 
Reduce cabozantinib by one dose level.               
 
At the discretion of the investigator, the dose can be interrupted and if blood pressure control is achieved, the dose does not have to be reduced if the physician wants to rechallenge with the same dose (i.e. physician discretion about reducing). If the same or higher BPs occur again than the dose should be interrupted, antihypertensives adjusted, and then the dose of cabozantinib should be reduced
 
 
 
Increase antihypertension therapy (i.e., increase dose of existing medications and/or add new antihypertensive medications).
 
Monitor subject closely for hypotension.
 
If optimal antihypertensive therapy (usually to include 3 agents) does not result in blood pressure <math>< 140</math> systolic or <math>< 90</math> diastolic, dose of cabozantinib should be reduced further by dose level increments.
 

$\geq 180$ mm Hg (systolic) OR $\geq 120$ mm Hg (diastolic)	
 
Interrupt treatment with cabozantinib. Add new or additional anti-hypertensive medications and/or increase dose of existing medications.
 
Monitor subject closely for hypotension.
 
When SBP <math>< 140</math> and DBP <math>< 90</math>, restart cabozantinib treatment at one dose level lower.
 
If optimal antihypertensive therapy (usually to include 3 agents) does not result in blood pressure <math>< 140</math> systolic or <math>< 90</math> diastolic, dose of cabozantinib should be reduced further by dose level increments.
 

Hypertensive crisis or hypertensive encephalopathy	Discontinue all study treatment
BP, blood pressure, SBP systolic blood pressure, DBP diastolic blood pressure NOTE: If SBP and DBP meet different criteria in table, manage per higher dose-modification criteria.	

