### **9.2 Evaluations During Treatment**

Evaluations may occur within a window of +/- 7 days. Assessments must occur on cycle 1, days 1, 8, 15, and 22, on Cycle 2, days 1 and 15, and on day 1 of all subsequent cycles as indicated in the Schedule of Evaluations ([Appendix I](#)).

- 9.2.1 Complete medical history and physical examination. To include vital signs, weight, performance status, adverse event evaluation). If hypertension (BP 140/90) is observed, decisions to decrease or hold the dose of study treatment must be based on BP readings taken by a medical professional and must be confirmed with a second measurement at least 5 minutes following the first measurement. (Refer to [Section 6.1.8](#) for management.)
- 9.2.2 CBC with differential and platelets, serum chemistry, amylase and lipase, and LFTs defined in [9.1.3](#).
- 9.2.3 Serum TSH. Testing should be performed every 4 weeks (every cycle) beginning Cycle 1 Day 1.
- 9.2.4 PT/INR and PTT. Testing should be performed every 8 weeks (2 cycles) beginning Cycle 1 Day 1.
- 9.2.5 CD4+ and CD8+ lymphocyte counts and HIV viral load. Samples will be obtained locally at time of Pharmacokinetic (PK) Specimen Collection on Cycle 1, Day 22, and at 12 week intervals while on study therapy.
- 9.2.6 Urine dipstick or urinalysis. Proteinuria seen on urine dipstick or UA should warrant urine protein/creatinine ratio (UPCR) determination and management according to [Section 6.1.9](#).
- 9.2.7 ECG and QTc assessments will be performed weekly during the first cycle of therapy, and day 1 of all subsequent cycles. Additional ECGs will be performed as indicated in [Section 6.1.16](#) (refer to [Appendix IX](#) for a list of drugs that may cause QTc prolongation).
- 9.2.8 CT scan for tumor measurement performed after every 2 cycles (every 8 weeks) of therapy for participants with solid tumors. Participants with cutaneous KS will not require CT scans.
- 9.2.9 KS participants will be evaluated for response after every other cycle according to the requirements in [Section 11.2](#). Chest x-ray will be performed as clinically indicated.
- 9.2.10 The participant will be given a copy of the participant diary to complete. Collect diary upon completion.
- 9.2.11 Correlative Studies (See [Section 10.0](#))

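### Section 6.1.8: the blood pressure target in the dose-reduction bullets joins its two limits with *or* where *and* is evidently meant, so a mandatory dose rule can be read two ways

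*Combined protocol and SAP*

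**What the plan says.** Section 6.1.8 manages hypertension through a table under one group heading, "Subjects not receiving optimized anti-hypertensive therapy". Apart from hypertensive crisis or encephalopathy, where treatment is discontinued, it has three blood pressure rows:

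- **Row 1** is entered when SBP is above 140 and below 160, or when DBP is above 90 and below 110. Antihypertensive therapy is increased and the cabozantinib dose is kept. The exception begins "If optimal antihypertensive therapy (usually to include 3 agents) does not result in blood pressure" and gives the target as <140 systolic or <90 diastolic. It adds a second trigger, "or if the subject is symptomatic, the dose of cabozantinib", and then calls for a reduction of one level.
- **Row 2** (SBP 160 to <180 or DBP 110 to <120) reduces one level at once or, at the investigator's discretion, interrupts. If the same target is missed, the "dose of cabozantinib should be reduced further by dose level increments".
- **Row 3** (SBP >=180 or DBP >=120) interrupts. When SBP is <140 and DBP is <90, the instruction is to "restart cabozantinib treatment at one dose level lower". The further-reduction bullet then repeats the *or* target.

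A note below the table says: "If SBP and DBP meet different criteria in table, manage per higher dose-modification criteria".

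**The concern.** The row is entered on either component, but its target, taken at its word, is met by either component. Every isolated systolic or isolated diastolic row 1 reading therefore satisfies the target on entry, before any antihypertensive is added. For those participants the blood pressure part of the bullet could never act.

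Two things are at stake. One is safety: section 7.1 lists hypertension as a likely (>20%) event for this drug, and a site taking the sentence literally would see no required reduction in this table after optimal therapy has failed on one component. The other is consistency of the primary endpoint. Sections 5.2 and 12.1 count a dose reduction required in Cycle 1 for a cabozantinib-related event as a DLT, and section 5.2 stops escalation at two DLTs in cohorts of 3 to 6. Two sites reading the bullet differently could classify the same participant differently.

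**Working it through.** The plan states no figure to reproduce. The check is logical, with a count of the readings affected.

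**Inputs** (section 6.1.8 table): row 1 entry SBP >140 and <160, or DBP >90 and <110; reduction target <140 *or* <90; restart criterion SBP <140 *and* DBP <90.

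**Trigger as written:** not(SBP <140 or DBP <90) = SBP >=140 **and** DBP >=90.

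**Trigger with *and*:** not(SBP <140 and DBP <90) = SBP >=140 **or** DBP >=90. This is the exact complement of the restart criterion.

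| On-treatment reading | In row 1 | Reduce, as written | Reduce, with *and* | Restart criterion met |
|---|---|---|---|---|
| 158/85 | yes | no | yes | no |
| 135/98 | yes | no | yes | no |
| 158/98 | yes | yes | yes | no |
| 140/85 | no | no | yes | no |
| 135/85 | no | no | no | yes |

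**Where the triggers disagree**, for whole-number readings below the row 2 limits:

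- SBP 140-159 with DBP at most 89: 160 - 140 = 20 systolic values.
- DBP 90-109 with SBP at most 139: 110 - 90 = 20 diastolic values.
- Exactly 140 or exactly 90 does not enter row 1. Removing those leaves 141-159 (19) and 91-109 (19).

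**Grid check.** Take SBP 100-159 and DBP 60-109 with DBP < SBP. Row 1 covers 1674 whole-number cells. With *and*, all 1674 trigger if they persist on optimal therapy. As written, only cells with both components raised do: 20 x 20 - 1 = 399, the 1 being 140/90, which is not in row 1. These counts describe the rule; they are not patient frequencies.

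**Does other text close the gap?**

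- The note on discordant components selects the row. At 158/85 only the systolic value meets a row, and that row's own bullet stays silent.
- The text of 6.1.8 interrupts dosing in severe cases "who cannot be controlled with medical interventions and discontinued in participants with hypertensive crises", but its lower limit is a sustained >=160 or >=110, above row 1.
- Symptomatic participants are reduced by the second half of the row 1 bullet.
- In rows 2 and 3 the literal reading also silences the further-reduction bullet (for example at 178/85 or 190/85). Those rows already reduce or interrupt, so the gap matters mainly in row 1.
- Table 6-1 lists interruption or dose reduction for related grade 2 events that are not easily managed. That covers part of the gap, but it is general guidance, and section 6.1 sends the reader to the specific guideline for hypertension.

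**The case against.** The strongest reply is that a negated *or* is ambiguous in ordinary English. Failing to reach <140 or <90 can mean failing either limit, which is the intended rule. The literal reading also defeats itself, since the bullet could never act on an isolated row 1 reading, and that points a sensible reader to the right meaning. This stands, and it is why the point is one of ambiguity. It does not remove the point: a mandatory dose rule should not rely on each site resolving its logic.

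Several stronger inferences are tempting, and the documents do not support them:

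- **That a site following the protocol must keep such a participant on full dose.** Table 6-1 offers interruption or reduction when a related grade 2 event is not easily managed, and blood pressure still raised on optimal therapy plausibly fits. The closing note's Cycle 1 exception concerns toxicity of lower grade than the table defines, so it does not remove this route.
- **That the table contradicts exclusion 3.2.15 or its own restart rule.** Exclusion 3.2.15, which treats >140 systolic or >90 diastolic as uncontrolled, governs entry to the study. The restart rule follows an interruption at >=180 or >=120, where a stricter condition could be deliberate. Both are evidence of intent, not conflicting instructions for the same event.
- **That DLT counts or the MTD are wrong as a result.** This would need a Cycle 1 event judged related, a reduction required under one reading only, and no other DLT criterion met. A related grade 3 non-hematologic event is a DLT whatever this table says. The CTCAE hypertension criteria are not in the documents, so the overlap cannot be settled.
- **That row 1 should also start at >=140 or >=90.** Section 9.2.1 does say "If hypertension (BP 140/90) is observed", but there it introduces the repeat-measurement requirement; it does not set a row limit. The present >140/>90 entry matches the eligibility limits. Lowering it would put an eligible participant stable at 140/85 on optimal therapy into row 1 and past the corrected target with no change in blood pressure.

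**Conclusion.** The wording defect is real and minor. All three bullets use *or*; the either-component row entry and the restart rule show that both components below their limits is meant. Under the literal reading, the required one-level reduction fails for asymptomatic row 1 participants with one raised component on optimal therapy: 19 systolic and 19 diastolic values, with the other component below its limit. An effect on DLT classification is possible but not shown, because the documents give no rate for such readings and no way to know how many sites would read the sentence literally. The conclusion rests on the text of the table alone and on no assumption about how often these readings occur.

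**What to change.** In all three reduction bullets, change *or* to *and* between the two limits, so that the target is <140 systolic and <90 diastolic. Leave the symptomatic clause in row 1 and the row 1 entry limits (>140/>90) as they are.

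This is a one-word edit in three places. Its cost is a few more required reductions: for example, asymptomatic 141/70 persisting on optimal therapy would now call for one, and so would a participant who entered row 1 and was brought down only to exactly 140 or exactly 90. Any such reduction in Cycle 1 for a cabozantinib-related event counts as a DLT under sections 5.2 and 12.1. If the study team does not want that, the DLT definition should say so.

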#### 6.1.9 Proteinuria

Proteinuria has been reported with approved drugs that inhibit VEGF pathways as well as with cabozantinib. Any level of proteinuria diagnosed by dipstick or urinalysis should be quantified by a UPCR (mg/dL protein / mg/dL creatinine). When a UPCR exceeds 1, a repeat UPCR or a 24-hour urine protein and creatinine should be performed to confirm the result. Cabozantinib should be

discontinued in participants who develop nephrotic syndrome (proteinuria  $>3.5$  g/day in combination with hypoalbuminemia, edema and hyperlipidemia) or any other relevant renal disease. Also, given the nephrotoxic potential of bisphosphonates, these agents should be used with caution in participants receiving treatment with cabozantinib. Details of management are described in the next Table below.

*Management of treatment emergent proteinuria*

Urine Protein/Creatinine Ratio	Action to Be Taken
$\leq 1$ mg/mg ( $<113.1$ mg/mmol)	
 
No change in treatment or monitoring.
 

$> 1$ and $< 3.5$ mg/mg ( $> 113.1$ and $< 395.9$ mg/mmol)	
 
Consider confirming with a 24-hour protein assessment within 7 days.
 
No change in cabozantinib treatment required if UPCR <math>\leq 2</math> mg/mg or urine protein <math>\leq 2</math> g/24 hours on 24-hour urine collection.
 
Dose reduce or interrupt cabozantinib treatment if UPCR <math>> 2</math> mg/mg on repeat UPCR testing or urine protein <math>> 2</math> g/24 hours on 24-hour urine collection. Continue cabozantinib on a reduced dose if UPCR decreases to <math>< 2</math> mg/mg. Consider holding cabozantinib treatment if UPCR remains <math>> 2</math> mg/mg despite a dose reduction until UPCR decreases to <math>< 2</math> mg/mg. Restart cabozantinib treatment at a reduced dose after a dose hold unless otherwise approved by sponsor.
 
Repeat UPCR within 7 days and once per week. If UPCR <math>< 1</math> mg/mg on 2 consecutive readings, UPCR monitoring can revert to protocol-specific times. (Second reading is confirmatory and can be done within 1 week of first reading.) If UPCR remains <math>> 1</math> mg/mg and <math>< 2</math> mg/mg for 1 month or is determined to be stable (<math>< 20\%</math> change) for 1 month, check urine protein/creatinine per protocol or as clinically indicated.
 

$\geq 3.5$ mg/mg ( $\geq 395.9$ mg/mmol)	
 
Hold cabozantinib treatment pending repeat UPCR within 7 days and/or 24-hour urine protein.
 
If <math>\geq 3.5</math> mg/mg on repeat UPCR, continue to hold cabozantinib treatment and check UPCR every 7 days. If UPCR decreases to <math>< 2</math> mg/mg, restart cabozantinib treatment at a reduced dose and monitoring of urine protein/creatinine should continue weekly until the UPCR decreases to <math>< 1</math> mg/mg. If UPCR remains <math>> 1</math> mg/mg and <math>< 2</math> mg/mg for 1 month or is determined to be stable (<math>< 20\%</math> change) for 1 month, check urine protein/creatinine per protocol or as clinically indicated.
 

Urine Protein/Creatinine Ratio	Action to Be Taken
Nephrotic syndrome	
 
• Discontinue all study treatment.
 

